[figure not shown]

# **Shifting Rehabilitation Paradigms in Skilled Nursing Facilities**

**NCT: 02927171**

**Version Date: 12.06.2018**

Each year Medicare spends approximately \$31.3 billion on 2.4 million skilled nursing facility (SNF) episodes of care. SNFs rely on interdisciplinary approaches to patient care to maximize rehabilitation potential for return to prior level of function and reduce the risk of adverse events in older adults. However despite a substantial increase in spending on SNF services and minimal change in complexity of the caseload, 68% of patients are below their pre-hospitalization level of function at discharge, 25% return to the community, and 18% are hospitalized. This may be partially explained by current SNF approaches to patient care which foster inactivity and participation in low intensity rehabilitation interventions (preliminary data). Both inactivity and low-intensity interventions may perpetuate further functional decline or impede maximal recovery. The serious implication of risk with functional decline is exemplified by studies which have shown declines in physical function can increase the risk of being re-hospitalized six-fold and may infer other long term effects such as increased risk for mortality, morbidity, and institutionalization. Muscle weakness, reduced cardiorespiratory reserve, and neuromuscular deficits have been attributed to this acute decline in function. However current rehabilitation strategies in SNFs do not promote adequate dose and mode of interventions to induce beneficial systemic adaptations, perhaps due to the lack of evidence on effective rehabilitation protocols for this medically-complex population. In addition, the lack of standardization across rehabilitation practices makes it difficult to discern which treatment approaches are the most effective. We propose to implement a standardized, progressive, multi-component program (PMC) to address this gap in research and clinical practice. The study will be completed concurrently in two SNFs and consist of three periods: 5 month pre-PMC training period, 2 month PMC training period, and 5 month post-PMC training period (Figure 1). We increased the data collection period from 3 to 5 months due to the variability in month to month census at the SNFs. The data from each facility will be pooled into the respective time period to dilute the effects of facility variability. Given the high turnover of patients in SNFs (average length of stay ~21 days), the analysis will consist of independent 2-sample t-tests. During pre and post PMC training periods, measures of physical function will be assessed on all patients weekly and at discharge from SNF. Any hospitalizations or emergency room visits and falls will be obtained from the medical record and documented. The discharge location of all patients will be documented. The length of stay will be recorded, but given the current reimbursement model, the average length of stay is not expected to change with implementation of PMC.

## I. Hypotheses and Specific Aims:

**Specific Aim 1:** To determine if the group in the post-PMC training period demonstrates better physical function, as measured by *gait speed* (primary outcome), timed-up-and go test (TUG), and the Short Physical Performance Battery (SPPB) compared to pre-PMC training period.

Hypothesis 1: Patients in the post-PMC training period will demonstrate greater improvements in gait speed, TUG, and SPPB at time of discharge from SNF (primary endpoint) compared to the group in the pre-PMC training period.

**Specific Aim 2:** To determine if the group in the post-PMC training period demonstrates improved rates of discharge to the community from SNF facilities and lower hospital re-admission rates compared to pre-PMC training period.

Hypothesis 2: Following the post-training PMC period, patients will demonstrate higher rates of discharge to the community and have a lower frequency of hospital re-admissions during SNF stay compared to the pre-PMC training period.

## II. Background and Significance:

### Increased Costs and Resource Allocation in SNFs

Following hospitalization, older adults experience rapid declines in functional mobility. Patients who are discharged to skilled nursing facilities (SNFs) participate in rehabilitation programs while being monitored by trained physicians and nurses to prepare for return to home or prior level of function. However, 24% of patients in a SNF will be readmitted to the hospital and 68% will be discharged at a lower level of function compared to pre-hospitalization levels, which calls for a change in current clinical practices across multiple health care providers in SNFs. Physical mobility has been suggested to be a strong predictor for hospitalization readmission; in fact those with lower levels of physical

activity are six times more likely to be re-hospitalized. Rehabilitation services provided by physical therapists (PTs), occupational therapists (OTs) and speech language pathologists (SLPs) have the potential to impact physical function outcomes, discharge to community, and rates of rehospitalization. Though these effects have not been consistently observed in combination under usual care or specifically attributed to therapy services. Observational data suggests patients are inactive more than 80% of the day and participate in conservative rehabilitation interventions over the course of their SNF stay, which may contribute to the persistently high rates of re-hospitalization, institutionalization, and poorer functional outcomes. The perpetuation of inactivity and use of conservative interventions presents an opportunity to develop and implement progressive, multi-component rehabilitation protocols that have the potential to impact practice patterns and outcomes in SNFs.

### **Lack of standardized care**

Currently, there is little standardization of overall care across facilities and regions, which likely contributes to varying outcomes and increased costs. SNF care consists of a multi-faceted approach from a variety of health care disciplines. Thus, attention to the quality of care from individual disciplines and interaction between disciplines could contribute to improvements in the overall care quality and subsequent outcomes. Rehabilitative therapy constitutes a pivotal role in facilitating a patient's return to previous level of activity and participation. However therapy sessions only comprise ~2-3 hours or 6-13% of a patient's day and are generally dosed at a poorly defined intensity. Therefore, greater concentration needs to be given to the quality and effectiveness of therapy interventions to induce greater gains within a shorter time. The reduced amount of time with a skilled therapist also diminishes the total activity or mobilization completed per day, which raises concern for further detrimental sequela stemming from immobility.

### **Limitations with Conservative Rehabilitation Approaches**

In the literature, the definition of treatment intensity is variable and ranges from a monitoring of total therapy time per session, time per activity, total therapy time per LOS, magnitude of activity counts with accelerometers or effort (% maximum). This evidence does give insight into the quality of the intervention and the amount of physiologic effort needed to complete activities. A preponderance of evidence exists which demonstrates the beneficial and safe effects of strength and aerobic training in older adults with and without chronic diseases. These benefits also extend to adults over 80 years old and frail individuals. In addition, the benefits of strength and aerobic training have been demonstrated in older adults with chronic conditions such as CHF, COPD, cancer, PVD, obesity, HTN, osteoporosis, CVA, dementia, osteoarthritis, hip fracture, joint arthroplasty, DM II, sarcopenia. Patients with the aforementioned conditions are commonly seen in SNF, though our observational data revealed limited use of strength and aerobic training principles during the course of usual care, which may impede maximal recovery of function. Furthermore, whether the beneficial effects of strength on function can be observed within the average 21 day stay in a SNF has yet to be evaluated. The focus on progressive, multi-component rehabilitation programs extends previous work being done by our lab which indicates increasing the complexity or effort during rehabilitation interventions-- including strengthening, balance and functional mobility training-- is safe, feasible, and improves outcomes in home and outpatient physical therapy settings. In our proposed study we will incorporate progressive strengthening, mobility, and aerobic interventions into a multi-faceted approach that provides carryover into performance of challenging functional tasks in multiple

environments. **This approach is novel in 1) the application of progressive exercise programs designed using the American College of Sports Medicine Guidelines to older adults in SNF settings and 2) the intervention occurs within current Medicare reimbursement guidelines for SNFs.**

### **Culture of Inactivity**

In addition to progressive therapeutic interventions, education and training on graded mobility guidelines for allied health disciplines (nursing, aides) will promote a culture of mobility to prepare patients for return home or decrease burden of care. A major goal of rehabilitation in the SNF setting is to prepare individuals for return to the community and presumably tolerate community levels of activity and participation. Low levels of physical activity have been connected to mortality rates and further health complications in acute care settings. That being said, evidence suggests patients in SNFs are ~80% less active compared to community-dwelling, older adults and, when active, do not engage in activity at a moderate intensity adequate for systemic adaptations. Barriers to mobilization by nursing staff may include perceived safety risk (falls, adverse acute events with exercise), staff shortages, lack of formal training on safety and equipment use, time constraints, etc. Nursing care directed at promoting independent self-cares and completion of exercise or walking programs may foster increased motor learning through high repetition practice, improved self-efficacy, and increased habitual activity. Enhanced motor learning, increased self-efficacy and improved mobility which can contribute to functional gains and increased preparedness in completion of instrumental and basic daily activities after discharge. **The implementation of a practical framework from which multiple disciplines can become involved in promoting activity outside of therapy sessions is a novel approach to reducing the detrimental sequelae stemming from the perpetuation of inactivity in SNFs.**

### **III. Preliminary Studies/Progress Report:**

#### **Preliminary Data in Home Health Settings**

Our research group has conducted a preliminary investigation on the feasibility and safety of implementing a similar PMC program during home physical therapy sessions (manuscript in review). Patients who receive home physical therapy are often medically-complex and at high risk for re-hospitalization, which makes this population comparable to the proposed SNF population.

For the preliminary work, patients were recruited from the University of Colorado hospital (n=22) and randomized into the PMC intervention group or usual care (UC). Treatment of both groups occurred over the course of ~30 days with a total of 8-10 treatment sessions, which is consistent with current reimbursement guidelines and home health practice. Measurements of gait speed and short physical performance battery (SPPB) were assessed at baseline, 30 days (end of treatment), and 60-day follow-up (primary endpoint). Preliminary data from this investigation provides compelling evidence that implementation of the PMC intervention results in 1) substantially improved physical function over a short duration, 2) sustainability of improvements at 30 and 60-days post discharge, and 3) no increased risk for injury.

**Results:** PMC resulted in a 60% improvement in function at 60 days compared to only 9.7% improvement with UC. For walking speed, a 0.1m/s difference in walking speed represents substantial meaningful change, and we saw differences almost **twice this large** in our preliminary data. In fact, 30% of patients in the PMC group achieved >1.0m/s

walking speed (threshold for independent community ambulation) at 60 days; no UC group patients achieved this walking speed threshold. A one-point difference in the SPPB represents substantial meaningful change, and we saw differences **twice this large** in our preliminary data. In fact, PMC resulted in a 60% improvement in function at 60 days compared to only 9.7% improvement with UC. Importantly, both groups received a comparable number of visits. In the usual care group there were 4 total episodes in (3 re-hospitalizations, 1 emergency room visit), while the PMC group had only 1 emergency room visit. Furthermore, these results provide evidence for the investigative team's experience managing medically complex patients using the proposed intervention strategy to promote favorable outcomes.

[figure not shown]
## **IV. Research Methods**

### **A. Outcome Measure(s):**

During both the pre-PMC and post-PMC training periods, a trained Certified Nursing Assistant (CNA) (blinded) will assess gait speed, TUG, and SPPB within 24-48 hours of admission to SNF. If the CNA is unable to assess within 24-48 hours of admission, then the physical therapist performs the assessments. The occupational therapist will administer the Mini Mental Status Scale to assess baseline cognitive status within 24-48 hours of admission to SNF. A trained CNA (blinded) will continue to perform functional assessments (gait speed, TUG, SPPB) weekly and at discharge from SNF (Figure 2). Physical therapists (PTs) and physical therapist assistants (PTAs) will perform weekly and discharge assessments as necessary.

Interventions: During the 5-month pre-PMC training period (baseline), all current patients at the SNF will receive usual care treatment as facility therapists will practice per current standard of care. We will collect pre-PMC training data for 3 months or until collection of data on 602 patients (half the number of patients approved to be consented) (Figure 1). Therapists will then be trained on the PMC intervention for 2 months. After training, the facilities and individual therapists will decide how to implement such care at their discretion. Following the training period, we will collect post-PMC training data for 5 months or until collection of data on 602 patients (half the number of patients approved to be consented) (Figure 1). The data collected in all facilities during the pre-PMC training period will be pooled into one group to dilute the effect of facility variability. The data collected during post-PMC training period will be pooled in the same way.

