### **Figure 2. Outcome Measure Assessments Time points**

Outcomes: All testing will occur at the SNF by facility PTs, PTAs, OTs or a trained CNA (blinded). Primary Outcome: **Gait speed** will be measured by the time it takes to walk a 4-meter path. Time will be measured with a stopwatch to the nearest hundredth of a second. This measure was selected as the primary outcome because: 1) it has been shown to predict risk of mobility and physical disability, higher health care utilization and increased mortality; 2) it has been established as a meaningful outcome measure in older persons with a wide range of conditions; 3) it is a valid and reliable measure; 4) it is easily understood by patients, their families, providers and health care policy makers (good face validity); and 5) it is easily performed in the home and well tolerated by patients varying in condition and degree of health. Secondary Outcomes: The **Timed Up And-Go (TUG)** test will be performed on each patient as a measure of basic mobility skill and evaluation of fall risk. The TUG test well established cut-off scores to indicate falls in both frail and community dwelling older adults. The TUG has excellent inter-rater reliability, and is responsive to changes in mobility status. The **Short Physical Performance Battery (SPPB)** is a well-accepted global measure of lower extremity function, which consists of walking speed, chair stands, and balance. It is a well-studied composite measure and a strong predictor of disability, institutionalization, and morbidity in older adults. The test takes ~10-15 minutes to administer and was designed to be administered in a setting with limited space. The battery has an excellent safety record as it has been administered to well over 10,000 persons in various studies. The SPPB components and total score are derived from normative values obtained from a population-based study. The reliability of the individual components, as well as the summary score of the SPPB, are good with intra class correlation coefficients (ICC) >0.88 and good sensitivity to change. The continuous scoring system minimizes ceiling effects and scores range from 0-12 with higher scores indicative of better performance.

Numbers and reasons for hospitalizations and emergency room visits during the SNF stay will be documented by treating therapists. Falls will also be counted and documented by

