treating therapists or nursing staff. Falls will be defined as an unintentional change in position resulting in coming to rest on the ground or other lower level.

Covariates, clinical and background characteristics. Information on other patient characteristics to describe the patient population and interpret results will be obtained from facility medical records; all data will be de-identified. These characteristics include age; gender; race; history of comorbidities, medications, primary diagnosis for hospital admission; length of skilled nursing facility stay; complications in hospital and length of stay.

Qualitative data will be collected through voluntary focus group discussions consisting of therapists in the SNFs with current IRB approval (Brookdale Mountain View, Veterans Community Living Center at Fitzsimons, PowerBack Rehabilitation, Gardens on Quail, Good Sam-Ambassador, Villa St. Louis Park). The data collected will inform future refinement of the PMC program for large-scale dissemination.

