### C. Study Design and Research Methods

This study is a preliminary investigation using a pre-post training design in six SNFs (Figure 1). We will pool the data across the six SNFs into the pre and post-PMC training periods to dilute the effect of facility variability. Given that the average length of stay in a SNF is 21 days, the pre/post PMC training design will consist of two independent samples of patients to include only those that were admitted and discharged within a given period. As we get interest from additional facilities, we may submit an addendum to include them. Additional sites would help inform sample size estimates for a potential future, cluster-randomization study design. During the 5-month pre-PMC training period, the rehabilitation therapists will treat patients per the current standard of care and a trained CNA (blinded) or PT/PTA (as necessary) will collect outcomes data at admission, weekly, and at discharge. Then, training on the PMC intervention will occur over a 2-month period. Any patients admitted or discharged in the SNF during the PMC training period will not be used. During the 5-month post-PMC training period, therapists will implement the PMC protocol and collect outcomes data as indicated previously (Figure 1).

The medical records will provide information on prior level of function, age, other medical conditions, **re-hospitalization** and **emergency room visits**, medications, sex, admitting diagnosis, **falls**, SNF length of stay, **discharge location**, evaluation and treatment documentation.

Five focus group discussions of 4-6 therapists each will follow an interview guide and last a duration of approximately 1 hour. Therapist participation is voluntary, and all participants will be asked for informed consent. Discussions will be recorded and transcribed for content analysis.

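### Therapists who deliver PMC may time their own patients' gait-speed tests, and the primary analysis has no check on who tested

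*Combined protocol and SAP*

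**What the plan says.** Section IV.A (Outcome Measure(s)) names the CNA as the usual tester after admission: "A trained CNA (blinded) will continue to perform functional assessments (gait speed, TUG, SPPB) weekly and at discharge from SNF". For admission it gives a fallback: "If the CNA is unable to assess within 24-48 hours of admission, then the physical therapist performs the assessments". For later tests it adds: "Physical therapists (PTs) and physical therapist assistants (PTAs) will perform weekly and discharge assessments as necessary". The Outcomes paragraph under the Figure 2 heading lists facility PTs, PTAs and OTs as well as the CNA as testers. Only the CNA is called blinded, and no section says to what.

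Section IV.C (Study Design and Research Methods) puts all time points under one rule for the pre-period: "a trained CNA (blinded) or PT/PTA (as necessary) will collect outcomes data at admission, weekly, and at discharge". For the post-period it says that "therapists will implement the PMC protocol and collect outcomes data as indicated previously". Between the periods, "Therapists will then be trained on the PMC intervention for 2 months".

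The primary outcome is a 4-metre walk timed by hand: "Time will be measured with a stopwatch to the nearest hundredth of a second". Section IV.F (Data Analysis Plan) compares mean change from admission to discharge between the two periods with one independent-sample t-test. It has no term for, and no sensitivity analysis by, the person who tested.

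**The concern.** The discharge walk is one of the two measurements in every change score. In a short, stopwatch-timed walk, the start and stop points and the encouragement given depend on the tester. After training, a stand-in therapist may know the programme, be delivering it and expect larger gains. The plan lets that person time their own patient.

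The comparison is between calendar periods, so anything about testing that changes from one period to the next is confounded with PMC. Two things could change: how often therapists stand in, and how they test when they do. Neither would be visible in the planned analysis. Section IV.F makes significance depend on that single test, so no other planned result would expose the problem.

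**Working it through.** **Inputs from the plan (Sample Size Estimates).** SD of change 0.29; target difference 0.14; 92 per group; one-sided alpha 0.05. Section IV.A gives a cap of 602 per period. The pilot values are labelled in feet. I assume m/s, because Preliminary Studies uses 0.1 m/s as the meaningful change and the sample size text uses 0.1 as the clinically significant difference.

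**The plan's own figure.** With SE = 0.29 × √(2/92) = 0.0428, a one-sided 5% t-test has 94.7% power for 0.14, not 90%. A one-sided test needs 75 per group for 90%. The stated 92 per group matches a two-sided 5% test (90.3%). That mismatch is a separate matter, and nothing below depends on it.

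**How a tester offset reaches the result.** Let b be the amount by which a therapist's recorded speed exceeds the CNA's for the same walk.

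| Admission tester | Discharge tester | Added to the change score |
|---|---|---|
| CNA | CNA | 0 |
| CNA | therapist | +b |
| therapist | CNA | −b |
| therapist | therapist | 0 if b is the same at both tests |

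Within a period, the mean change shifts by (therapist share at discharge × b at discharge) − (therapist share at admission × b at admission). The bias in the comparison is the post-period shift minus the pre-period shift. It is zero if shares and offsets are equal in both periods. It can take either sign.

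**Illustration (shares and offsets are assumed).** Take net shift = share × offset, where the share is post-period patients tested by the CNA at admission and a therapist at discharge. Set the pre-period shift to zero.

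- 10% × 0.05 = 0.005 m/s
- 20% × 0.05 = 0.010 m/s
- 20% × 0.10 = 0.020 m/s

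SE is 0.0428 at 92 per group and 0.29 × √(2/602) = 0.0167 at 602. The smallest significant differences are 1.653 × 0.0428 = 0.071 and 1.646 × 0.0167 = 0.0275. With no true PMC effect, the false-positive rate is the upper-tail probability of a noncentral t with noncentrality shift/SE:

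| Net shift (m/s) | 92 per group | 602 per group |
|---|---|---|
| 0 | 5.0% | 5.0% |
| 0.005 | 6.3% | 8.9% |
| 0.010 | 7.9% | 14.8% |
| 0.020 | 11.9% | 32.7% |

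A larger sample does not dilute such a shift. It makes a given shift more likely to reach significance.

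**Power of a CNA-only analysis for 0.14 (one-sided 5%).** If 80% of 92 per group qualify (74), power is 90%. If half qualify (46), it is 74%.

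**The case against.** **The plan already intends the CNA to test.** The stand-in sentence follows directly after the one naming the CNA, so its natural meaning is back-up when the CNA cannot test. That stands. Half of the proposed rule makes this reading explicit. The part about testing one's own patients is new.

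**The rules do not clearly differ by time point.** A reader might infer from Section IV.A that admission has a firm trigger and discharge an open one, which would tilt the bias towards therapist testing at discharge. Section IV.C applies the looser wording at admission too, so the documents do not support that. The reverse sequence, therapist then CNA, is equally allowed and has the opposite sign.

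**The same procedure applies in both periods.** Section IV.A says so, and no section shows that the mix changes. This also stands. Every shifted row of the illustration sets the pre-period shift to zero, which is an assumption. Training could still alter therapists' expectations under an unchanged procedure.

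**Tester role may be recorded anyway.** The covariate list ("These characteristics include age; gender; race; history of comorbidities, medications, primary diagnosis for hospital admission; length of skilled nursing facility stay") and the medical-record list in Section IV.C cover patient and record items, not form fields. Section IV.D mentions a study-specific data dictionary and audit trails. Absence from the lists therefore does not show that role goes unrecorded. What remains is that no planned analysis uses it.

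**This is a preliminary study meant to inform a later one.** That justifies back-up testers. It is not a reason to leave tester role out of the analysis.

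**Conclusion.** The point holds as a gap in safeguards. Therapists delivering PMC may time their own patients' primary-outcome test, and the single unadjusted t-test would pass any between-period difference in tester mix or behaviour straight into the estimated effect. The documents show neither that such a difference exists nor which way it would run.

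The illustrative error rates, about 6% to 12% at 92 per group and 9% to 33% at 602, rest on an SD of 0.29, units of m/s, a net shift in favour of PMC and no shift in the pre-period. With equal shares and offsets in both periods the rate stays at 5%.

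Two stronger readings should be resisted. One is that the CNA is in fact unblinded because aides receive mobility training (Culture of Inactivity): the text does not say whether the assessing CNA attends. The other is that the result is biased in favour of PMC: nothing in the plan establishes a direction. The changes below are worth making because they are cheap, not because bias has been shown.

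**What to change.** 1. **Testing rule.** At sites that have not begun their pre-period, replace the open wording in Sections IV.A and IV.C with: a PT or PTA tests only when the CNA is unavailable, and does not test a patient they treat if another qualified tester is on shift. Apply the same rule in both periods. Do not introduce it between periods at a site already collecting data, because that would itself change the tester mix. Sample Size Estimates describes Powerback as not yet started and accounting for 800 of the 1,234 requested (800/1,234 = 65%). If that text is still current, the rule could cover most of the requested enrolment.
2. **Tester role.** Record CNA, non-treating PT/PTA or treating PT/PTA at every gait-speed test. For data already collected, recover the role from existing forms where possible. Tabulate it by period and time point.
3. **Sensitivity analysis.** In Section IV.F, prespecify one supportive analysis: the primary t-test in patients tested by the CNA at both admission and discharge. The primary test is unchanged.

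It would also help to state what the CNA is blinded to. I would not ask that the CNA be kept out of mobility training, since aides are part of the programme's intended audience.

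**Cost.** One field per test, one table and one extra analysis, with no extra staff, patients or visits. The rule may occasionally delay a test. The CNA-only subset is smaller and selected, so it can support the primary result but not replace it. The CNA will still know the calendar period.
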